### 301 **Control/covariate variables**

302 These will be recorded at the beginning of the study to help reduce error variance in the  
303 dependent measures:

- 304 1) Time elapsed since diagnosis of Type 1 DM (ratio variable)
- 305 2) Age (ratio variable)
- 306 3) Physician attending each patient – there are 3 physicians (nominal).
- 307 4) Whether each patient started with CSII by pump or insulin degludec (nominal)
- 308 5) Race of patient (if there is any variability; unlikely) (nominal).

309

### 310 **Statistical Analysis**

311 Statistical analyses will be performed using STATA version 15.0, revision 25, released  
312 September 2017. ([www.stata.com](http://www.stata.com))

313 Since all the dependent variables are interval and the independent and control/covariate  
314 variables are a mixture of ratio and nominal, a General Linear Model for Repeated Measures  
315 analysis can be used. Depending on the final sample sizes a hierarchical stepwise analysis could  
316 be performed to identify the more useful control/covariate variables.

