## 114 **STUDY TYPE**

115 This will be a randomized, cross-over, open label, single-center study consisting of a 20 week  
116 period on each of two basal insulin delivery methods, both in combination with insulin aspart  
117 with boluses taken by insulin pump. Each 20 week period will consist of a 4 week insulin  
118 optimization period for titration of basal and bolus insulin doses, followed by a 16 week  
119 maintenance period. The final 2 weeks of the maintenance period during each treatment arm  
120 will be used for endpoint data collection. The treatment sequence will occur in random order.  
121 The study population will include patients with type 1 diabetes with good baseline glycemic  
122 control who are experienced in the use of both CSII and CGM; the cross-over design allows each  
123 subject to serve as his or her own control.

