## 229 **ASSESSMENTS OF SAFETY:**

230

231 Hypoglycemia will be captured by fingerstick BG and by CGM. All episodes of severe  
232 hypoglycemia (requiring assistance) will be documented and reported as AE’s in diaries.  
233 Categories of hypoglycemia that will be captured include: percent time in two categories of  
234 hypoglycemia (BG < 54 mg dl and 55-69 mg/dl) by CGM, episodes of symptomatic BG-confirmed  
235 hypoglycemia (<54 mg/dl), nocturnal hypoglycemia and severe hypoglycemia. In the event  
236 where the SMBG and the CGM readings are discordant, the SMBG will be considered the  
237 primary source.

238

239 Time to recovery from hypoglycemia, defined as BG  $\geq$  70 with resolution of symptoms, during  
240 each treatment will also be captured.

241

242 **OTHER ASSESSMENTS**

243

244 Patient satisfaction with each study treatment will be assessed by TRIM-D and TRIM-DD  
245 questionnaires.

246

247 **ASSESSMENT OF SUBJECT COMPLIANCE**

248

249 Compliance of study subjects with use of CSII and CGM will be assessed by review of device  
250 downloads which capture percent time devices are used, set changes, boluses and  
251 carbohydrate intake. Since subjects will be using their insulin pumps to bolus, all bolus insulin  
252 doses and carbohydrate intake will be captured in both treatment arms by review of insulin  
253 pump downloads at each study visit.

254

255 Compliance with administration of basal insulin during the degludec treatment arm will be  
256 assessed by documentation of insulin doses and times in subject diaries. Number of missed  
257 injections will be captured during the degludec treatment arm; number of infusion set changes,  
258 set occlusions, and missed boluses will be captured during both treatment arms.

259

260 **STATISTICAL CONSIDERATIONS**

261

262 **Sample Size Determination**

263 The subjects in a recent study (4) should closely reflect the population we are going to study.  
264 Using the statistics from that source as an estimate of population parameters, power analyses  
265 were done for: (1) percent time in euglycemia (BG 70 to 180 mg/dl), desired effect size 0.4, (2)  
266 SD of BG by CGM, desired effect size 0.44, and (3) HbA1c, desired effect size 0.44. The repeated  
267 independent variable is degludec vs CSII. These a priori analyses – using G\*Power, version  
268 3.1.9.2 <http://www.gpower.hhu.de/en.html> – assumed a Type I error of .05 and a power of .85  
269 (Type II error of .15).

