270

271 The sample size estimate required for percent time in euglycemia was the largest at n = 47.  
272 Allowing for a 10% dropout rate a final sample size of 53 will be sought – more if possible.

273

274 **Statistical Methods**

275

276 Ho: For Type 1 DM subjects using degludec vs CSII, there is no difference between mean  
277 percent time in euglycemia, mean SD of BG by CGM, or mean HbA1c.

278

279 Ha: For Type 1 DM patients using degludec vs CSII, there will be mean differences between  
280 percent time in euglycemia, SD of BG by CGM, and HbA1c. (No one tailed tests are planned.)

281

282 **Dependent Variable**

283 One group of patients will first use degludec for 20 weeks then switch to CSII for 20 weeks. As  
284 all eligible patients who sign the IRB consent form are identified, a random number will be

285 generated to determine the treatment with which they begin first. The other group of patients  
286 will start with CSII and after 20 weeks switch to Tresiba for 20 weeks. Randomization sequence  
287 will be determined by computerized randomization program. All patients will receive both  
288 treatments unless they drop out. Dropouts are unlikely since the participants are all regular  
289 continuing patients of the site's clinical practice.

290  
291 Since each patient will be measured twice - insulin degludec vs CSII by pump – this repeated  
292 measure will be the dependent variable.

293 Since study participants are all ongoing patients of the three physicians at the site, there should  
294 be no missing data, per-protocol, or intention-to-treat issues. Only patients who complete the  
295 entire 46-week study will be used in the final analysis.

296  
297 No continuous or ratio variables will be categorized.

298  
299 No interim analysis will be performed.

300

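### The protocol does not state whether starting order is crossed with treatment, so it is left open whether the primary crossover comparison is adjusted for period

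*Protocol*

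**What the plan says.** The trial is a randomised two-period crossover with 20 weeks on each treatment (Study Type). Under Sample Size Determination the repeated "independent variable is degludec vs CSII". The Dependent Variable text repeats this: "Since each patient will be measured twice - insulin degludec vs CSII by pump".

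Starting order appears under Control/covariate variables as item 4 of five: "Whether each patient started with CSII by pump or insulin degludec (nominal". The other four are diabetes duration, age, physician and race. The stated purpose of all five is to lower error variance.

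The Statistical Analysis section names the model permissively ("variables are a mixture of ratio and nominal, a General Linear Model for Repeated Measures" analysis can be used) and adds: "Depending on the final sample sizes a hierarchical stepwise analysis could" be run to find the more useful covariates. Starting order is not exempted from that search. No period term, treatment-by-order term or carry-over term is named.

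On allocation, a random number is "generated to determine the treatment with which they begin first", and the sequence "will be determined by computerized randomization program". Blocking is neither stated nor excluded.

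**The concern.** In a two-treatment, two-period crossover, the period effect is the treatment-by-order interaction. Starting order has one value per patient. As a main effect it therefore explains differences between patients but drops out of each patient's degludec-minus-CSII difference. An analyst could enter it, believe that order had been dealt with, and have changed nothing in the primary comparison.

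A period shift is possible here. Doses are optimised again after crossover and diabetes education is given at every visit. If a shift exists and period is left out, two things follow. The shift adds to the error variance of the paired differences, which costs power. If the two sequences differ in size, part of the shift also enters the treatment estimate. Sequence sizes among analysed patients may differ even under blocked allocation, because dropouts are not replaced and only completers are analysed.

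**Working it through.** **Inputs.** From the protocol: n = 47 (53 with dropout), effect size 0.4, type I error 5%, power 85%, no one-tailed tests. Assumed: the shift sizes, simple randomisation where averages over splits are given, and 0.4 read as SDs of the within-patient difference unless stated.

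**1. The plan's own figure.** A paired t-test with effect 0.4 and 85% power needs n = 47 one-sided (power 85.5%) and n = 59 two-sided. Two-sided, 47 also arises from a repeated-measures ANOVA with f = 0.2 and correlation 0.6, but no correlation is stated. For dropout, 47/0.9 = 52.2, rounded up to 53. The two-sided paired test at n = 47 has power 76.6%, which is the base level below. That gap from 85% is a separate matter.

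**2. Algebra.** Let τ be the treatment effect, π the shift from first to second period, n1 the degludec-first patients, n2 the CSII-first patients, N = n1 + n2, and σ the SD of the differences.

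- Expected difference: τ − π if degludec is first, τ + π if CSII is first. A main effect of order adds the same amount to both of a patient's values and cancels.
- Without period: mean = τ − π(n1 − n2)/N; variance of differences = σ² + π²·4n1n2/N².
- With period: average of the two sequence means = τ; SE = (σ/2)√(1/n1 + 1/n2) on N − 2 degrees of freedom, against σ/√N on N − 1.

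Fraction of the shift entering the unadjusted estimate: 1/47 = 0.02 at 24/23; 7/47 = 0.15 at 27/20; 13/47 = 0.28 at 30/17.

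SE with σ = 1: 0.1459 without period; with period 0.1459 at 24/23 and 0.1475 at 27/20.

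**3. Model check.** One simulated 30/17 dataset with a built-in shift and no treatment effect, fitted by mixed models:

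| Terms | Treatment estimate | SE |
|---|---|---|
| treatment | −0.284 | 0.174 |
| treatment + order | −0.284 | 0.174 |
| treatment + order + period | −0.119 | 0.160 |
| treatment × centred order | −0.119 | 0.160 |

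The interaction was 1.198, so the estimated shift is 1.198/2 = 0.599. Then 0.599 × 13/47 = 0.166, which is the gap between the two estimates apart from rounding.

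**4. Power averaged over simple randomisation** (simulation, n = 47, effect 0.4, two-sided 5%):

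| Shift (SD) | Without period | With period |
|---|---|---|
| 0 | 76.5% | 75.6% |
| 0.2 | 74.9% | 75.5% |
| 0.3 | 73.1% | 75.7% |
| 0.4 | 70.3% | 75.6% |

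Average type I error without period at a 0.4 SD shift is 5.0%.

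**5. Particular splits** (degludec-first/CSII-first), shift 0.3 SD:

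| Split | Without period | With period |
|---|---|---|
| 24/23 | 72.3% | 76.5% |
| 23/24 | 75.3% | 76.7% |
| 27/20 | 63.4% | 75.6% |
| 20/27 | 82.6% | 75.6% |

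Under simple randomisation, a split at least as uneven as 27/20 has probability 0.38.

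**6. Other readings.** If 0.4 is in raw SDs with correlation 0.6 (assumed), the effect is 0.4/√(2 × 0.4) = 0.447 and the base power 85.1%. At a 0.3 SD shift, 27/20 gives 74.3% without period against 84.2% with; 20/27 gives 89.5% against 84.3%. The pattern is unchanged.

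If the 10% improvement under Study Population means 10 percentage points and equals 0.4 SD (assumed), the SD is 25 points. A 0.3 SD shift is then 7.5 points and moves a 27/20 estimate by 7.5 × 7/47 = 1.1 points.

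**The case against.** The strongest reply is that nothing has been fixed wrongly. Model terms and coding are usual SAP content, and no separate SAP is at hand. The protocol records the one variable that a period adjustment needs and lists it for the model. In the multivariate form of a repeated-measures General Linear Model, each between-patient term is fitted to the within-patient difference as well. Order coded +1/−1 then gives exactly the period-adjusted estimate. This stands: the text leaves the adjustment open and does not rule it out. A reader might infer that the plan makes order a patient-level main effect only, but the documents do not say so.

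The case for a large shift is also weak. The optimisation after crossover mirrors the one after randomisation: Study Type gives each period a 4-week "optimization period for titration of basal and bolus insulin doses, followed by a 16 week" maintenance period. Education starts at screening, the endpoint is read in the last 14 days of each period, patients are experienced and well controlled, and recruitment over 6 to 9 months partly spreads calendar effects. At a 0.1 SD shift, omitting period costs nothing on average (76.0% without, 75.4% with). This stands too.

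What remains is that the protocol does not simply defer the model. It names the repeated factor, the covariates, their purpose and a selection method. Under those words, order is an optional error-reducing covariate that may be dropped.

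**Conclusion.** The point holds as a low-severity one. The protocol leaves open whether the primary comparison is adjusted for period, and two of the three routes it permits (order as a main effect, or order dropped) do not adjust. On average the stake is about 3 points of power or less for shifts up to 0.3 SD at n = 47. A movement of the estimate needs both a real shift and unequal sequences. The size of any shift is an assumption throughout.

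Two stronger readings are not supported. A reader might infer inflated type I error, since at a 0.4 SD shift it is 9% for a 30/17 split. That needs a shift as large as the target effect and a split whose probability, that uneven or worse, is 0.08 under simple randomisation; the average is 5.0%, and blocking is not excluded. A reader might also infer that stepwise selection itself damages the primary test. Selection of a crossed term would do little harm; what matters is that order can drop out.

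**What to change.** Add to Statistical Analysis: the primary repeated-measures model always includes treatment, period (first or second 20 weeks; equivalently, treatment crossed with centred starting order) and sequence, with patient as the blocking or random factor; these terms are kept regardless of significance and are exempt from any stepwise selection.

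The planned General Linear Model can stay, and starting order is already recorded. No patients or visits are added.

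The cost is one degree of freedom. If there is no period effect, power falls by about 0.1 point at a 24/23 split. Averaged over simple randomisation it falls by about 1 point: 76.5% to 75.6% at n = 47, and 81.6% to 80.8% at n = 53.

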### 317 **DATA HANDLING AND RECORD KEEPING**

318 The study data (CGM data and laboratory endpoints including HbA1c and GlycoMark) will be  
319 uploaded and stored in the cloud in HIPAA-compliant electronic files. Pertinent data for  
320 endpoint safety and efficacy analyses will be entered into and electronically filed in password-  
321 protected Excel spreadsheets. Hypoglycemia diaries will be on paper and stored as source  
322 documents along with paper CRF's capturing study-related procedures (history, physical exam,

323 vital signs, con meds, AE's) at each visit. Patients will complete TRIM-D and TRIM-DD  
324 questionnaires, and responses will be tabulated into Excel spreadsheets for statistical analysis.

325 All paper source documents and CRFs will be stored on site. All electronic data will be stored in  
326 the cloud in HIPAA-compliant electronic files.

### 327 **ETHICAL CONSIDERATIONS**

328 The sponsor (Mountain Diabetes and Endocrine Center), its investigators and site staff will  
329 comply with all applicable regulatory and legal requirements, ICH GCP guidelines and the  
330 Declaration of Helsinki in obtaining and documenting the informed consent.

331 Informed consent will be obtained by a medically qualified site member (MD or RN) after each  
332 subject has had time to review the informed consent document and have any questions about  
333 the study answered. This is performed in a conference room at the study site in a private and  
334 unhurried fashion. The subjects may bring family members with them to witness the informed  
335 consent process. The informed consent documents will be paper documents that will be  
336 retained at the site, signed by the subject and investigator, and a copy will be provided to each  
337 subject.

338 Upon approval of the study protocol, the study will be submitted for approval to IntegReview  
339 IRB in Austin, Texas for review and approval. The informed consent document will include  
340 information about the IRB and contact information for the IRB, the site, and the study principal  
341 investigator.

342 The study will be conducted in accordance with ICH GCP guidelines and the Declaration of  
343 Helsinki.

### 344 **STUDY SCHEDULE**

345 Planned recruitment period: 6 to 9 months

346 Expected milestones: Start of study: immediately upon IRB approval (March 2018)

347 First patient first visit (FPFV): within 1 week of IRB approval (site is ready to begin recruitment  
348 with subjects available to start upon protocol and IRB approval and obtaining study insulin)

349 Last patient first visit (LPFV): within 6 to 9 months of FPFV

350 Last patient last visit: 46 weeks after LPFV

351 Estimated study duration (FPFV to LPLV): 14 months (March 2018 to May 2019)

352 Completion of final study report: within 6 weeks of study completion

353 Time to submission of study for publication: within 12 weeks of study completion

### 354 **STUDY DRUGS AND MATERIALS**

355 Study medication: insulin degludec (Tresiba) U100 or insulin degludec (Tresiba) U200 (Novo  
356 Nordisk) with insulin aspart (administered as bolus insulin via insulin pump) (Novolog, Novo  
357 Nordisk) for one treatment arm; insulin aspart (Novolog) administered by CSII for both basal  
358 and bolus insulin in second treatment arm.

359 Study Devices: subjects' own insulin pumps will include Medtronic (530, 730 models; no low  
360 blood glucose suspend models or closed loop pumps will be used), Animas Ping, Animas Vibe,  
361 Tandem T-slim and Insulet Omnipod.

362 The study CGM will be Dexcom G5 or G6.

### 363 **PACKAGING AND LABELLING OF STUDY MEDICATION AND DEVICES**

364 Study insulins (insulin degludec and aspart) will be distributed at study visits to each subject  
365 from the site. Insulin degludec will be supplied in injection pens (5 per box for U100 and 3 per  
366 box for U200). Insulin aspart will be supplied in vials (as bolus insulin will be administered via  
367 insulin pump.) Subjects will use their own insulin pumps and pump supplies during the study.  
368 Dexcom sensors will be supplied for a two week period (using one sensor weekly) at baseline  
369 and for the final two weeks of each treatment period. These will be distributed and placed at  
370 CGM dispensing/insertion site visits (see study visit flow sheet).

### 371 **STORAGE AND DRUG ACCOUNTABILITY OF STUDY MEDICATION**

372 Study insulins will be received in temperature-controlled containers and the temperature of the  
373 medication upon receipt will be recorded. Study insulins will be stored at the study site in  
374 refrigerators maintained between 2 and 8 degrees Celsius; the temperature will be monitored  
375 and recorded daily. No trial medication will be dispensed to any individual not enrolled in the  
376 study. All medication used in the study will be recorded in the CRF at each study dispensing  
377 visit. Subjects will be provided with sufficient study insulin for study completion.

378 Subjects will be instructed not to refrigerate opened insulin degludec (Tresiba U100 & U200)  
379 and to store the product at room temperature. Properly stored opened insulin degludec can be  
380 used for up to 8 weeks (7). Subjects may choose to refrigerate or not refrigerate an opened vial  
381 of insulin aspart (Novolog), maintaining the vial at a temperature of less than 86°F (30°C) for up  
382 to 4 weeks (8).

### 383 **AUXILIARY SUPPLY**

384 Study subjects will use their own insulin pumps and insulin pump supplies.

385 Dexcom glucose sensors (6 per subject) will be purchased by the site and supplied to subjects  
386 for two weeks at 3 times (baseline and for the final two weeks of each treatment period).  
387 Subjects will use their own CGM receiver devices which will be downloaded at appropriate  
388 study visits. Site will have back up receivers to supply to subjects in case of loss or malfunction  
389 of subject's own device (not likely). Subjects will use their own sensors for each treatment  
390 period except for the 3 two week periods of CGM data capture as described above.

391

392

### 393 **RANDOMIZATION AND BLINDING**

394 This is an unblinded study as the two basal insulin delivery methods (degludec via injection vs.  
395 aspart via CSII) cannot be blinded. For a description of the randomization and treatment  
396 allocation, please refer to the Statistical Methods section above.

### 397 **CONCOMITANT ILLNESSES AND MEDICATIONS**

#### 398 **Definitions:**

399 Concomitant illness: any illness that is present at the start of the trial (at the first study visit).

400 Concomitant medication: any medication other than the trial product(s) that is taken during the  
401 trial, including the screening and run-in periods.

402 Details of all concomitant illnesses and medication will be recorded at trial entry (at the first  
403 study visit). Any changes in concomitant medication will be recorded at each visit.

404 The information collected for each concomitant medication will include start date, stop date or  
405 continuing, and indication.

406 For each concomitant illness, date of onset, date of resolution or continuing, will be recorded.

407

## 432 **DEFINITIONS**

### 433 **Adverse Event (AE):**

434 An AE is any undesirable medical event occurring to a subject in a clinical trial, whether or not  
435 related to the trial product(s). This includes events reported from the first trial related activity  
436 after the subject has signed the informed consent and until post treatment follow-up period as  
437 defined in the protocol. This will also include any events related to the malfunction of a  
438 medical device (i.e. an insulin pump or Dexcom CGM). The following will not be recorded as  
439 AEs, if recorded as medical history/concomitant illness on the CRF at screening:

- 440 • Pre-planned procedure, unless the condition for which the procedure was planned has
- 441 worsened from the first trial related activity after the subject has signed the informed consent
- 442 • Pre-existing conditions found as a result of screening procedures

### 443 **Clinical Laboratory Adverse Event:**

444 A clinical laboratory AE is any clinical laboratory abnormality regarded as clinically significant,  
445 i.e. an abnormality that suggests a disease and/or organ toxicity and is of a severity which  
446 requires active management, (i.e. change of dose, discontinuation of trial product, more  
447 frequent follow-up or diagnostic investigation).

448

### 449 **Serious Adverse Event (SAE):**

450 A serious AE is an event that results in any of the following:

- 451 • Death
- 452 • A life-threatening\* experience
- 453 • In-patient hospitalization or prolongation of existing hospitalization
- 454 • A persistent or significant disability/incapacity
- 455 • A congenital anomaly/birth defect
- 456 • Important medical events that may not result in death, be life-threatening\*, or require
- 457 hospitalization may be considered an SAE when, based upon appropriate medical judgement,
- 458 they may jeopardise the subject and may require medical or surgical intervention to prevent
- 459 one of the outcomes listed in this definition. Suspicion of transmission of infectious agents
- 460 must always be considered an SAE.

461 \*The term life-threatening in the definition of SAE refers to an event in which the subject was at risk of death at  
462 the time of the event. It does not refer to an event which hypothetically might have caused death if it was more  
463 severe.

464

